Effect of HRV-B on PTSD among Combat Veterans. In 2010, we examined the effects of HRV-B on combat Veterans with PTSD in a small pilot study at DVAMC ($n=10$). In our published findings, we reported that HRV-B significantly improved HRV coherence as well as measures of attention and immediate memory (ATTN/IM).⁴⁴ In our current DoD-funded research, baseline PTSD symptoms were not significantly different between the active and sham training groups (Table 1). Linear mixed model analysis⁵⁴ of PTSD rating (CAPS) for the Training Group by Time interaction was statistically significant, $F(5, 127)=2.60, p=.028$; furthermore the Pre- to Follow-up difference within the HRV-B group was significant. Paired t-test within the HRV-B group of Pre- to Follow-up was statistically significant, mean=16.7, $t(12)=4.66, p=0.001$ ($\eta_p^2=0.663$). These treatment effect was well beyond the accepted reliable change score of 12 points reduction in CAPS⁵⁵; a reduction of 15 points on the CAPS is considered clinically beneficial.⁵⁶ These results indicate that PTSD severity was reduced by HRV-B training compared to the Sham group, and the benefit persisted for 8 weeks after training ended.

Training	CAPS	Pre-	Post-	8-week Follow-up
Sham	Mean	76.1	69.9	72.9
	SE	4.3	5.2	7.1
	n	32	23	18
HRV-B	Mean	77.5	53.1	60.8
	SE	3.7	7.7	7.7
	n	29	16	12

[figure not shown]
Effect of HRV-B on Depression in Combat Veterans with PTSD. Depression (BDI-II) was also measured in our current DoD-funded research. The repeated measures contrast of Group x Time for the effect of HRV-B on Depression for Pre- to Post-Training was statistically significant, ($F(1,28)=6.29, p=0.02 (\eta_p^2=0.173)$). The reduction in BDI-II in the HRV-B group compared to Pre-training was statistically significant, (mean=5.9, $t(16)=1.82, p(1\text{-tail})=.045 (\eta_p^2=0.180)$), while the BDI-II change in the Sham training group was not, $p(1\text{-tail})=.23$. These results indicate that depression was reduced by the HRV-B treatment compared to the Sham training at the Post-Training assessment. A change of 5 points in the BDI is considered to be a reliable and clinically significant change.⁵⁷

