2.3 Data Analysis Plan

Statistical Power & Sample Size. Preliminary data for HRV coherence and the pain (BPI), and stress (PSS) scales from our HRV-B pilot study among DVAMC chronic pain patients were used to estimate statistical power for the proposed primary study outcomes (HRV coherence, pain rating, negative emotion, activity limitation, perceived stress scale). Two-sided, two sample t-tests were used for the statistical power calculations. The analysis for the proposed study will use more sophisticated methods that tend to reduce variance in the dependent variables and thus increase power, thus what is presented here is likely conservative. An overall significance level of 0.05 was used with correction for multiple testing via the Bonferroni method for the 5 outcomes (adjusted significance level = 0.01; 0.05/5). Our pilot data indicate that at baseline, no statistical differences were observed between treatment groups for any outcome. The detectable effect differences between treatment and sham groups with corresponding standard deviations are presented in Table 3. We assumed equal variances in the differences between pre- and post-treatment comparisons for both groups. A sample size of 25 in each group will attain a statistical power of at least 84.5% to detect the expected effect differences between treatment groups, and groups sizes of 40 patients will provide statistical power exceeding 95% for comparisons between treatment groups for each outcome. Thus, a sample size of 40 patients per group would achieve ample statistical power even with retentions on of 55-60%.

Table 3. Estimated Power for Differences Between HRV-B Treatment & Sham Interventions

Sample Size per Group	Negative Emotion (4.5±10; 15.5±10)*	Activity limitation (4± 9.5; 14± 9.5)*	Pain Rating (1.8±5.0; 10±5.0)*	Perceived Stress (-1.2±4.5; 4±4.5)*	HRV Coherence (-0.03±0.15; -0.20±0.15)*
22	82.3%	78.1%	99.6%	86.5%	84.9%
25	88.1%	84.5%	99.9%	91.4%	90.2%
30	94.1%	91.7%	99.9%	96.2%	95.4%
40	98.7%	97.9%	99.9%	99.3%	99.1%

*Average pre-post change ± SD in the control group; and average pre-post change ± SD in the treatment group, respectively

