We will use "intention to treat" (ITT) analyses on all subjects without regard to level of compliance. ITT analysis is based on the assumption that once a subject is randomized to a group, data for that subject will enter into the final analysis. ITT assumes unrelated treatment events are equally likely across groups and that outcome data are complete. All data from non-adherent and dropout subjects are included; therefore, ITT provides conservative effect estimates. ITT is most appropriate for randomized, controlled clinical trials involving lengthy treatment protocols when an effective treatment arrests progression of disease. Because recommendations for treatment of primary and secondary outcomes will likely continue to include care (i.e., controls still receive usual care), ITT analysis will better reflect what will be observed if HRV-B is introduced into clinical practice. This analysis answers the question: What is the effect of HRV-B on outcome measures in a situation where individuals range from fully compliant to non-compliant? In this pilot intervention, however, we also are interested in the actual effect of HRV-B on the outcomes. In ancillary analyses, we will perform multiple imputations for subjects with missing data (see below). These *post hoc* analyses will answer the question: What is the effect of full HRV-B training on the outcomes? This will provide a more accurate picture of HRV-B effects because it focuses only on subjects who completed the training.

Missing Data. Inevitably, missing data will arise and a variety of approaches will be considered to address this issue. First, our integrated team will meet and discuss the hypothesized nature of the missingness mechanism.¹⁰⁸ For example, if the subjects have data that are missing completely at random or missing at random (MAR) then multiple imputation (MI) procedures can be used (e.g., "PROC MI").¹⁰⁹ When missingness is suspected to be non-ignorable, then a model for the missingness mechanism must be employed.^{110,111} In all models, sensitivity analyses will be performed to test the robustness of the estimates to the missing data assumption (if any). We will create a number of locked datasets (e.g., 10) with imputed values that will be used in all analyses that require MI. This will ensure that all MI analyses are based on the same imputed data.

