his or her participation, the assigned treatment will be stopped. We will encourage any patients who have their assigned treatment stopped to maintain attendance at their training visits even without treatment, and attempt to collect the evaluation data on the appropriate schedule. Follow-up would be stopped if the subject advises us that he or she wishes to terminate all participation in the research. During the consent process, the subject will be told that cessation of follow-up can be voluntarily obtained by signing a form requesting that no further contact be made. They also will be informed that termination of their participation will not impact their usual care at the DVAMC.

The DVAMC uses a Research Compliance Officer (RCO) as the clinical trial monitor who performs audits of consent forms, reporting and regulatory compliance, and documentation according to Standard Operating Procedures of the VA Office of Research and Development, and the local DVAMC Research office. The monitor reports separately from the IRB structure. The monitor will also perform random audits on any trial including the proposed study.

Data Accuracy and Protocol Compliance. Subject eligibility forms will be completed on all subjects to assure appropriate subjects are recruited. Biofeedback Certification Institute of America (BCIA) certification of training and skill in HRV-B or its equivalent will be required of the HRV-B professional. This research will follow the HRV-B training protocol adopted by the BCIA. Protocol compliance integrity will be monitored by supervision and communication between the biofeedback professional, research staff, and the Co-PIs.

Literature Cited

1. Simon LS. Relieving pain in America: A blueprint for transforming prevention, care, education, and research. *Journal of Pain and Palliative Care Pharmacotherapy*. 2012;26(2):197-198.

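### The plan calls its ITT estimate conservative because dropout data are included, but it expects missing outcomes, and unmeasured HRV-B leavers can inflate the estimate

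*Combined protocol and SAP*

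**What the plan says.** All statements below are in section 2.3 unless noted.

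- **ITT.** Everyone randomised is analysed whatever their compliance, and the plan concludes: "All data from non-adherent and dropout subjects are included; therefore, ITT provides conservative effect estimates". The sentence just before it gives the condition: "ITT assumes unrelated treatment events are equally likely across groups and that outcome data are complete". The question set for this analysis is the effect of HRV-B when patients vary in how far they comply.
- **Retention.** The sample-size paragraph says that 40 per group gives "ample statistical power even with retentions on of 55-60" per cent.
- **Missing data.** "Inevitably, missing data will arise and a variety of approaches will be considered to address this issue". Multiple imputation is offered under missing (completely) at random, a model of the missingness mechanism if it is thought non-ignorable, and sensitivity analyses in all models. The choice follows a team discussion; no primary assumption or specific method is named.
- **Multiple imputation.** It is placed among ancillary, post hoc analyses of the effect of full training, which are said to concern only patients who finished training.
- **Main model.** Linear mixed models for repeated measures, with group, time and their interaction. Three change scores per patient are described, although the model equation refers to assessment time points.
- **After stopping treatment (section 2.4).** Staff will encourage attendance and "attempt to collect the evaluation data on the appropriate schedule". Follow-up ends if the patient withdraws from all participation.

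**The concern.** With outcomes measured in everyone, non-compliance dilutes the contrast. ITT then understates the effect of full training, and the word *conservative* is fair. The plan does not have that situation. An outcome that was never collected cannot be included.

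A patient who leaves before the post-training visit and is not seen again has no change score. If the model is fitted to raw visits, that patient contributes only baseline. In both cases the estimate rests on leavers having the course of those who stayed in their arm. For HRV-B leavers who did not complete training, that credits them with the trained effect. The result then moves towards the effect of full training, while the plan describes it as the effect across all levels of compliance.

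At stake is how a positive result is read. A reader told that the estimate is conservative will treat it as a cautious figure for offering HRV-B in clinic, when it may be too high.

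**Working it through.** **1. The plan's own figures reproduce.** Two-sided two-sample t-test, noncentral t, alpha from "adjusted significance level = 0.01; 0.05/5". The least-powered outcome in Table 3 is activity limitation: difference 14 − 4 = 10, SD 9.5.

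| Per group | Table 3 | Recomputed |
|---|---|---|
| 22 | 78.1% | 78.1% |
| 25 | 84.5% | 84.5% |
| 30 | 91.7% | 91.7% |
| 40 | 97.9% | 97.9% |

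Retention of 55-60% is 0.55 × 40 = 22 to 0.60 × 40 = 24 per group, so 16-18 of 40 patients may lack data. The power figures are not in error. They address precision and say nothing about bias from who is missing.

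**2. Illustration for pain.** Inputs: Table 3 gives mean changes of 10 (HRV-B) and 1.8 (sham), so D = 8.2. Assumptions, not given in the documents: D is the effect in stayers, leavers are unmeasured, and leavers keep a fraction f of the benefit. With r the HRV-B retention:

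all-assigned effect = D × [r + (1 − r) × f]

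| r | f | All-assigned effect | 8.2 ÷ effect |
|---|---|---|---|
| 0.55 | 0 | 8.2 × 0.55 = 4.5 | 1.82 |
| 0.60 | 0 | 8.2 × 0.60 = 4.9 | 1.67 |
| 0.55 | 0.5 | 8.2 × 0.775 = 6.4 | 1.29 |
| 0.60 | 0.5 | 8.2 × 0.80 = 6.6 | 1.25 |
| any | 1 | 8.2 | 1.00 |

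If leavers benefited more than stayers (f above 1), the all-assigned effect would exceed 8.2 and the bias would run the other way.

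**3. Does the mixed model behave this way?** A random-intercept model was simulated with 40 per arm, four visits, all baselines kept, a stayer effect of 1 SD and f = 0 (150 runs). With 55% retention in both arms, the true all-assigned effect was 0.55 SD and the mean estimate 1.03 SD (simulation SE 0.03). Keeping the baseline values did not remove the inflation, and equal retention did not protect against it. Sham retention does not enter the formula in step 2 either.

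**The case against.** **The plan is not silent.** It promises sensitivity analyses and a model for non-ignorable missingness, and it tries to keep measuring patients who stop. Each value obtained after stopping reduces the problem. This stands as mitigation. It does not rescue the claim, because no assumption or method is fixed and nothing specified tests the direction of bias.

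**55-60% is a tolerance in the power argument, not a forecast.** True. The chronic pain pilot (section 1.1) reports 100% retention, though with 14 patients and no sham arm. Because Table 3 draws on that pilot, 8.2 is not documented as a stayers-only effect; treating it as one is an assumption.

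**The sponsor's PTSD trial might be read as showing heavier loss under HRV-B.** Table 1 has data on 29, 16 and 12 HRV-B patients and 32, 23 and 18 sham patients: 55% against 72% at post-training, 41% against 56% at follow-up. The documents do not support that reading. The table is cited to show that "baseline PTSD symptoms were not significantly different between the active and sham training groups (Table 1") and to report symptom scores, not retention. The trial is in progress and its baseline counts equal enrolment to date, so some patients may not have reached later visits. The differences are compatible with chance (Fisher p = 0.19 and 0.31), and the population has PTSD. The counts are at most a warning.

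**A reader might also put 41% into the formula and infer 2.4-fold inflation at 8 weeks.** That would give no benefit to at least 16 − 12 = 4 patients whose post-training assessment had already been done. It should not be used.

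**No section says the result will be reported as a lower bound.** Also true. The claim sits in a rationale paragraph, and deleting it alone changes no analysis.

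**Conclusion.** The statement that ITT is conservative does not follow from the plan and contradicts the condition stated in the sentence before it. The main estimate can be inflated for the question that the plan itself sets. For pain, the illustration gives 8.2 against 4.5-4.9 if leavers change like sham, or 6.4-6.6 if they keep half the benefit, at 55-60% HRV-B retention. These figures rest on three assumptions: 8.2 applies to stayers, leavers are unmeasured, and leavers do worse than stayers. Without the last there is no inflation, and the bias can reverse. The point is that the direction is unknown, not that inflation is shown. It does not depend on unequal dropout between arms.

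A separate error is the statement that the imputation analyses concern only patients who finished training. Imputation fills in patients with missing data; it does not restrict the analysis to completers.

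Severity: should-fix. This is a self-described pilot with missing-data work already promised, but the claim affects how its result will be read.

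**What to change.** 1. Delete the clause that draws the conservative conclusion, and make no such claim in reports. Agreement between a primary and a sensitivity analysis would show robustness, not conservatism.
2. State that the ITT effect covers all assigned patients, uses every value obtained after treatment stops (section 2.4), and takes missing at random as its primary assumption.
3. Correct the statement that multiple imputation concerns only completers.
4. For each primary outcome, pre-specify one sensitivity analysis in which HRV-B patients with no later data are imputed from the sham arm (reference-based imputation). A tipping-point analysis would also serve. Report it beside the primary result.
5. Tabulate retention and reasons for leaving by arm and visit. The plan already tabulates missing values, summarises reasons for non-compliance and tracks attrition, so this is a small addition.

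The cost is SAP wording and one more imputation run, with no new data. The reported effect may look less favourable.

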Random Assignment to the 6-week HRV-B treatment or sham intervention group will occur following the baseline assessment. We will use a permuted block randomization procedure, with a block size of 4 and no stratification. Thus, for example, assuming 20 patients are to be assigned either to Sham (S) or Biofeedback, there would be 20 blocks of 4 patients, and two patients will be assigned each to the (S) treatment and two to the biofeedback by randomly selecting one of six possible permutations of the two treatments in blocks of four. The order of the blocks will be randomly generated. The treatment assignment will be determined before any patient is enrolled into the study and the documentation and assignment of patients will be kept confidential and known only to the PI ([name]). Only the Biofeedback professional, who delivers the treatment, will know the treatment status of the participant; other study personnel will be blinded to treatment status.

HRV-B Training. HRV-B training will follow our previously established, standardized protocol that is consistent with recommendations of the Biofeedback Certification Institute of America (BCIA), consisting of a 15-minute resting period that includes HRV recording, and a 25-minute biofeedback training and coaching or sham period. The resting periods are the same for both the HRV-B treatment and sham groups. Participants will be affixed with HRV monitoring equipment and will be instructed to sit quietly for 15 minutes in a relaxed posture, viewing a static nature scene on a computer monitor, without any instruction, coaching or biofeedback. Coaching or instruction will start after the 15-minute resting period. Patients in the sham condition will be asked to 'just relax' or 'take it easy' for the remainder of the 25-minute session. Patients in the HRV-B group will be coached on how to achieve HRV coherence.

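### The plan describes the same ancillary analyses as imputation for missing data and as completers only; these conflict as written, and neither supports calling the result more accurate than ITT

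*Combined protocol and SAP*

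**What the plan says.** Section 2.3 (Statistical Analyses) makes ITT on all subjects, whatever their compliance, the main approach. It then gives a second interest: "In this pilot intervention, however, we also are interested in the actual effect of HRV-B on the outcomes". Consecutive sentences describe how this will be met:

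- The method: "In ancillary analyses, we will perform multiple imputations for subjects with missing data".
- The question these post hoc analyses are to answer: "What is the effect of full HRV-B training on the outcomes".
- The justification: "This will provide a more accurate picture of HRV-B effects because it focuses only on subjects who completed the training".

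The Missing Data paragraph that follows offers multiple imputation when data are MCAR or MAR, calls for a model of the missingness mechanism when it is suspected to be non-ignorable, and adds: "In all models, sensitivity analyses will be performed to test the robustness of the estimates to the missing data assumption". A fixed number of imputed datasets (10 is the example) will be locked: "This will ensure that all MI analyses are based on the same imputed data".

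Two other places matter. On timing, Section 2.2 states: "Random Assignment to the 6-week HRV-B treatment or sham intervention group will occur following the baseline assessment". On follow-up, Section 2.4 says that patients whose assigned treatment is stopped will be encouraged to "maintain attendance at their training visits even without treatment, and attempt to collect the evaluation data on the appropriate schedule".

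**The concern.** The linking words in Section 2.3 tie the imputation, the full-training question and the restriction to completers to the same analyses. An analyst could not tell from this text whom to include.

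The reason given for the accuracy claim is the restriction to completers. Training follows randomisation, so completing it is a post-randomisation event, and comparing completers across arms gives up the protection of randomisation. The arms differ in what is asked of patients: active coaching and a handheld device in one, passive relaxation and a stress ball in the other. Equal selection therefore cannot be taken for granted.

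At stake is how a secondary result is read. The text sets a conservative ITT estimate against an actual effect, which invites readers to trust the ancillary figure over the randomised comparison.

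**Working it through.** The plan gives no figure for these analyses, so there is none to reproduce. The check compares what each reading would estimate.

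**Inputs from the document.** 40 per arm; 55-60% retention contemplated (Section 2.3, Statistical Power); Pain Rating change 1.8 in control and 10 in treatment, SD 5.0 (Table 3), so a planned difference of 8.2; post-training assessments in the ongoing PTSD study, 16 of 29 active and 23 of 32 sham (Section 1.1).

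**Assumed, not in the document.** Completion rates for this trial, how completion depends on outcome, and the share of the effect that non-completers keep.

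**Reading 1: completers only, no true effect.** Let improvement be N(0,1) in each arm. The probability of completing is logistic in improvement with slope b = 0.5 or 1.0 (odds multiplied by exp(0.5) or exp(1.0) per SD), and the intercept is set to give completion c. The completers' mean improvement M(c,b) follows by numerical integration:

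| c | b = 0.5 | b = 1.0 |
|---|---|---|
| 60% | 0.189 | 0.332 |
| 62.5% | 0.178 | 0.312 |
| 70% | 0.143 | 0.253 |
| 80% | 0.096 | 0.173 |
| 90% | 0.049 | 0.091 |

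The bias is the active-arm value minus the sham-arm value:

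- Equal completion and slope, or everyone completes: 0.
- Same slope, active completion 10 points lower: 60% vs 70%, 0.046 and 0.079; 80% vs 90%, 0.047 and 0.082.
- Same slope at the PTSD study's assessment proportions (55.2% vs 71.9%): 0.078 and 0.133. That study was ongoing, so these counts are not clean dropout.
- Selection in the active arm only, 62.5%: 0.178 and 0.312.
- Opposite selection, 60% vs 70%: 0.189 + 0.143 = 0.332 and 0.332 + 0.253 = 0.585.

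Reversing the selection reverses the sign. On Pain Rating, 0.046-0.082 SD × 5.0 = 0.2-0.4 points (3-5% of 8.2). Active-arm-only selection gives 0.9-1.6 points (11-19%), and opposite selection gives 1.7-2.9 points (20-36%).

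**Reading 2: imputation.** Let c be active-arm completion, p the share of the full effect that non-completers keep, and q the share of non-completers whose outcomes are observed. With imputation by arm under MAR, and completion unrelated to outcome apart from the lost effect:

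estimate / full-training effect = [c + (1 − c)qp] / [c + (1 − c)q]

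At c = 0.6:

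| q | p = 0 | p = 0.5 |
|---|---|---|
| 1 | 0.60/1.00 = 60% | 0.80/1.00 = 80% |
| 0.5 | 0.60/0.80 = 75% | 0.70/0.80 = 88% |
| 0 | 100% | 100% |

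So what imputation estimates depends on how far the follow-up effort in Section 2.4 succeeds. Observed outcomes are left unchanged, and no separate imputation for the full-training question is described.

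**The case against.** **The sentences can be reconciled.** Imputing missed later assessments among training completers would remove the mechanical conflict. That stands as a possible intention, but the plan does not say it, and the result would still be a subset selected after randomisation.

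**Imputation may answer the full-training question.** A reader might infer that it never can. The document does not support that. Section 2.4 promises only encouragement and an attempt at collection, for patients whose treatment is stopped, and the sample-size text contemplates substantial loss. If non-completers are mostly unassessed and MAR holds, the estimate moves towards full training. Even then, the plan's stated reason, the focus on completers, would not describe the analysis.

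**The bias may be nil.** The pain pilot reports 100% retention, and eight veterans completed its HRV-B arm. With full completion the issue disappears. A pilot of that size does not assure this, and the plan itself allows for retention of 55-60%.

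**Completion is measured in other ways.** The plan does not define completion by sign-in sheet. Section 2.2 also records visit number and duration, home practice, device data and HRV coherence. The lack of a stated completion threshold is missing detail and does not carry this point.

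**It is ancillary and post hoc.** This is true and limits the severity. It does not correct the stated rationale.

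**Conclusion.** Wrong as written, of modest severity, and confined to the ancillary analysis. The two descriptions conflict, and the accuracy claim rests on a restriction that removes the protection of randomisation.

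The size is uncertain because the completion mechanism is assumed. The completers-only bias is zero under equal selection or full completion, 3-5% of the planned pain difference in the mild same-slope case, and several times larger if selection differs between arms. A reader might take 0.18-0.31 SD, or even 0.33-0.59 SD, as a worst case. Neither is: other slopes and completion rates would give other values.

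A reader might also infer that the trial's main result is compromised, or that the team has committed to publishing a completers-only figure as the actual effect. The document supports neither. ITT remains primary, its mixed model and the power figures are untouched, and the text expresses an interest in the actual effect without fixing a reporting label.

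**What to change.** 1. Separate the two analyses. Use the planned imputed datasets, on all 80 randomised subjects, for the ITT question. Under MAR they share much of the mixed model's assumption, so rely on the non-ignorable models and sensitivity analyses already foreseen in the Missing Data paragraph as the real test of it.
2. Delete the sentence "This will provide a more accurate picture of HRV-B effects because it focuses only on subjects who completed the training", and do not report a completers-only result as the actual effect of HRV-B.
3. Label any completers-only comparison as descriptive and subject to post-randomisation selection.

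The cost is a few sentences of analysis-plan wording and one relabelled analysis, with no added patients or data. If the team still wants a full-training effect, that is a separate choice needing its own stated assumptions and possibly its own imputation or model; this fix does not depend on it.
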